## 6. PROCEDURES

The study will be conducted in compliance with the ICH of Technical Requirements for Registration of Pharmaceuticals for Human Use/GCP and applicable regulatory requirements. The following administrative/demographic procedures will be conducted as outlined in the Table of Events ([Table 5](#)). Waivers to the protocol will not be granted during the conduct of this trial, under any circumstances.

Any questions regarding the protocol should be directed to the Amgen Medical Monitor or designee.

### **Informed Consent**

An ICF must be signed by the subject before any study-related assessments are performed. Details of the informed consent process may be found in [Section 13.3](#).

### **Inclusion / Exclusion Criteria (Eligibility Criteria)**

Subjects must meet all inclusion criteria ([Section 4.2](#)) and must not have any of the conditions specified in the exclusion criteria ([Section 4.3](#)) to qualify for participation in the study. The subject's source documents must support his/her qualifications for the study (eg, if a female subject does not require pregnancy testing and birth control because of a hysterectomy, the date of the hysterectomy must be included in the medical history).

### **Medical and Disease History**

Relevant medical history should be recorded, including smoking and alcohol history, as well as previous relevant surgeries (please refer to the electronic Case Report Form (eCRF) Completion Guidelines for further details). Disease history includes history of PPP and PAO.

### **Prior/Concomitant Medications and Therapies**

All medications and therapies being taken/used by the subject at the time of consent or at any time during the study should be recorded. Other key medications and therapies, such as previous treatment for TB or relevant diseases, should be recorded. Please refer to the eCRF Completion Guidelines for additional instructions.

All medications and therapies for PPP used within the last 5 years prior to the randomization, including topicals, systemics, and all other therapies, should be recorded. The stop dates for all medications and therapies prohibited in the study should be recorded. Responses to prior PPP therapies should also be recorded. Please refer to the eCRF Completion Guidelines for additional instructions.

### **6.1. Screening Period**

Screening evaluations will be performed for all subjects to determine study eligibility. These evaluations must be completed within 28 days of Baseline (Visit 2) unless noted otherwise below.

Safety laboratory analyses will be performed by the central laboratory. Screening laboratory values must demonstrate subject eligibility, but exclusionary results may be re-tested one time

within the screening window, without Amgen Medical Monitor approval. Subjects who fail initial screening may re-screen one additional time for the study.

The following assessments will be performed at screening as specified in the Table of Events ([Table 5](#)), after informed consent has been obtained:

- Demographics (year of birth, sex, race, and ethnicity-if allowed by local regulations)
- Complete medical history (all relevant medical conditions diagnosed/ occurring prior to screening should also be included)
- Disease history (including specific information regarding diagnosis, date of diagnosis, negation of plaque-type psoriasis, and of presence of pustular psoriasis in any part of the body other than the palms and soles).

The following information is also included:

- Presence or absence of focal infection, ie, periapical pathosis, periodontitis, Angina and Sinusitis
- Smoking History (years/amount) and Current Status (Yes/No and average packs/day)
- Presence or absence of regular dental examination (eg, annually at least)
- Presence or absence of PAO
- Dental Examination and Evaluation of necessity of treatment for focal infection
  - To conduct medical examination by dentist at Screening and obtain data if there is any dental focal infection (eg, chronic periapical periodontitis, chronic marginal periodontitis) or not,
  - To evaluate the necessity of treatment (any endodontic treatment for periapical pathosis [eg, infected root canal treatment, tooth extraction], and periodontal surgery for moderate to severe periodontitis).
  - Investigators should evaluate whether a treatment for focal infection is preferred to enrolment in the study.
- Prior/Concomitant Medications and Procedures
  - Inadequate response to PPP by treatment with topical steroid and/or topical vitamin D3 derivative preparations should be confirmed.
  - Prior and concomitant medications/procedures except for PPP and focal infection should be recorded including all procedures occurring  $\leq$  28 days prior to the baseline.
  - History of treatment for focal infection should be recorded within 24 weeks prior to the baseline.
  - All medications and therapies for PPP used within the last 5 years prior to the randomization, including topicals, systemics and all other therapies, should be recorded.

- AE/SAE assessment (begins when the subject signs the informed consent form)
- Psychiatric evaluation
- Serum Pregnancy test is required for all female subjects of childbearing potential. Serum beta human chorionic gonadotropin ( $\beta$ -hCG pregnancy test will be performed).
- Counseling about pregnancy precautions and the potential risks of fetal exposure must be conducted.
- Hepatitis B and C
- Vital signs
- Height and Weight
- Complete physical examination
- Clinical laboratory evaluations
  - Hematology/Chemistry
  - Urinalysis
- PPPASI (see [Section 6.4.1](#))
  - If obvious improvement during screening ( $\geq 5$  PPPASI total score improvement) is observed at randomization, the initiation of study treatment is not permitted.
  - Efficacy assessments may be performed by the qualified physician who has completed the training for efficacy evaluation.
- Examination for other Inclusion / Exclusion Criteria

Randomization is performed via Interactive Response Technology (IRT).

## 6.2. Treatment Period (Placebo-controlled phase and Active treatment phase)

The subject will begin treatment upon confirmation of eligibility. The subject must start treatment within 28 days of signing the informed consent form (ICF). For subsequent visits, an administrative window of  $\pm 2$  days until Visit 10 (Week 16) and  $\pm 4$  days for Visit 11 to 14 (Week 20 to 32) are permitted respectively. If screening assessments are performed within 72 hours of Baseline Visit, physical examinations and clinical laboratory evaluations, except for Immunology and Inflammation, need not be repeated at Baseline.

Treatment will occur as described in [Section 7.3](#).

During the treatment period:

- Subjects must complete all SROs prior to any other study procedure being performed.
- Subjects should complete the questionnaires in the following order when applicable:
  - 1) Subject's VAS assessment for PPP symptoms for hands and feet, 2) Subject's assessment for PPP signs/findings, 3) DLQI, 4) EQ-5D.

- Efficacy assessments may be performed by the qualified physician who has completed the training for efficacy evaluation at any time during a study visit, but only after the subject has completed all SROs assessments, when required.
- The physician performing efficacy assessments shall make independent observations at a given study visit and shall not review previous assessments or subject-derived data in advance of conducting the assessments.

The following evaluations/assessments will be performed at the frequency specified in the Table of Events ([Table 5](#)).

- Status of smoking
- Concomitant medications and procedures evaluation
- AE/SAE evaluation (continuously)
- Psychiatric evaluation
- Pregnancy test for FCBP
  - Urine dipstick pregnancy test will be performed at Baseline (within 72 hours prior to the first administration of IP) and Visit 10 (Week 16). An unscheduled urine pregnancy test should be conducted administered if the subject has missed a menstrual period. See [Section 6.5.3](#).
- Contraception education for FCBP
- Vital signs
- Weight
- Complete or limited physical examination
- Clinical laboratory evaluations
  - Hematology/Chemistry
  - Immunology/Inflammation
- Efficacy assessment (see [Section 6.4](#))
  - PPPASI, PPSI, PGA and modified PPPASI
- Subject reported outcomes or quality of life questionnaires (see [Section 6.7](#))
  - Subject's VAS assessment for PPP symptom, Subject's assessment for PPP signs/findings,
  - DLQI, EQ-5D

### 6.2.1. End of Treatment

An end of treatment (EOT) evaluation will be performed on Visit 14 (Week 32) or for subjects who are withdrawn from treatment for any reason as soon as possible after the decision to permanently discontinue treatment has been made.

For Visit 15 (4 Weeks After Last Dose), an administrative window of  $\pm$  7 days is permitted.

The following evaluations will be performed as specified in the Table of Events ([Table 5](#)):

- Status of smoking
- Concomitant medications and procedures evaluation
- AE/SAE evaluation (monitored through 28 days after the last dose of IP)
- Psychiatric evaluation
- Pregnancy test for FCBP
  - Urine dipstick pregnancy test will be performed.
- Vital signs
- Weight
- Complete physical examination (source documented only)
- Clinical laboratory evaluations
  - Hematology/Chemistry
  - Immunology/Inflammation
- Efficacy assessment (see [Section 6.4](#))
  - PPPASI, PPSI, PGA and modified PPPASI
- Subject reported outcomes or quality of life questionnaires (see [Section 6.7](#))
  - Subject's VAS assessment for PPP symptom, Subject's assessment for PPP signs/findings,
  - DLQI, EQ-5D

### 6.3. Follow-up Period

All subjects will be followed for 28 days after the last dose of IP for AE reporting, as well as any serious adverse events (SAEs) made known to the Investigator at any time thereafter, as described in [Section 10.1](#).

### **6.3.1. Observational Follow-up Visit**

Observational Follow-up evaluation will be performed on 28 days after last dose of IP. An administrative window of  $\pm$  7 days is permitted.

During the observational follow-up period;

- Subjects must complete all SROs prior to any other study procedure being performed.
- Efficacy assessments may be performed by the qualified physician who has completed the training for efficacy evaluation, but only after the subject has completed all SROs assessments.
- The physician performing efficacy assessments shall make independent observations at a given study visit and shall not review previous assessments in advance of conducting the assessments.

The following evaluations will be performed as specified in the Table of Events ([Table 5](#)):

- Concomitant medications and procedures evaluation
- AE/SAE evaluation (monitored through 28 days after the last dose of IP)
- Psychiatric evaluation
- Vital signs
- Weight
- Limited physical examination
- Clinical laboratory evaluations
  - Hematology/Chemistry
  - Immunology/Inflammation
- Efficacy assessment (see [Section 6.4](#))
  - PPPASI, PPSI, PGA and modified PPPASI
- Subject reported outcomes (see [Section 6.7](#))
  - Subject's VAS assessment for PPP symptom, Subject's assessment for PPP signs/findings

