### **6.5.3. Serum and Urine Pregnancy Tests for Females of Childbearing Potential (FCBP)**

A serum pregnancy test with a sensitivity of  $\leq 25$  mIU/mL will be required for FCBP subjects at screening. In addition, a urine pregnancy test will be performed at the site on all FCBP subjects at the Baseline Visit, Visit 10 (Week 16) and Last Treatment Visit (Visit 14 [Week 32]). An unscheduled urine pregnancy test should be performed if the FCBP subject has missed a menstrual period. If positive results are obtained from a urine pregnancy test, a serum pregnancy test should be performed to confirm, and if positive results are obtained from a serum pregnancy test, IP should be discontinued. The event must be reported (See [Section 10.4.1](#)).

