All AEs (non-serious and serious) will be recorded by the Investigator from the time the subject signs informed consent until 28 days after the last dose of IP as well as SAEs made known to the Investigator at any time following the protocol-required reporting period or after end of study. All AEs (serious/ non- serious) will be recorded on the CRF and in the subject's source documents. All SAEs must be reported to Amgen Global Patient Safety within 24 hours of the Investigator's knowledge of the event using the paper Serious Adverse Event Report Form (refer to [Appendix J](#)) by facsimile/email of the paper SAE Form directly to Amgen Global PatientSafety.

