### 10.4.1. Females of Childbearing Potential (FCBP) – Collection of Pregnancy Information

Pregnancies and suspected pregnancies (including elevated  $\beta$ -hCG or positive pregnancy test in a FCBP regardless of disease state) occurring while the subject is on IP, or within 28 days of the subject's last dose of IP, are considered immediately reportable events. If positive results are obtained from a serum pregnancy test, IP is to be discontinued immediately and the subject instructed to return any unused portion of the IP to the Investigator. The pregnancy, suspected pregnancy, or positive pregnancy test must be reported to Amgen Global Patient Safety immediately by email, phone or facsimile, or other appropriate method, using the Pregnancy Notification Form, or approved equivalent form in English language. (refer to [Appendix K](#)). The Pregnancy Notification Form in English language must be submitted to Amgen Global Patient Safety within 24 hours of learning of a subject's pregnancy. (Note: Sites are not required to provide any information on the Pregnancy Notification Form that violates the country or regions local privacy laws).

After obtaining the female subject's signed consent for release of pregnancy and infant health information, the investigator will collect pregnancy and infant health information and complete the pregnancy questionnaire for any female subject who becomes pregnant while taking IP through 28 days of IP. This information will be forwarded to Amgen Global Patient Safety. Generally, infant follow-up will be conducted 12 months after the birth of the child (if applicable)..

The female subject may be referred to an obstetrician-gynecologist or another appropriate healthcare professional for further evaluation.

The Investigator will follow the female subject until completion of the pregnancy and must notify Amgen Global Patient Safety immediately about the outcome of the pregnancy (either normal or abnormal outcome).

If the outcome of the pregnancy was abnormal (eg, spontaneous abortion), the Investigator should report the abnormal outcome as an AE. If the abnormal outcome meets any of the serious criteria, it must be reported as an SAE to Amgen Global PatientSafety via the paper Serious

Adverse Event Report Form in English language within 24 hours of the Investigator's knowledge of the even.

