11.1. Adverse Events

Adverse events will be analyzed in terms of treatment-emergent adverse events (TEAEs) which are defined as any AEs that begin or worsen on or after the first dose of IP through 28 days after the last dose of IP or study treatment discontinuation date, whichever is later. All AEs will be classified using the Medical Dictionary for Regulatory Activities (MedDRA) classification

CC-10004 (Apremilast)

Statistical Analysis Plan. Protocol CC-10004-PPP-001

system version 21.1 or higher. Unless otherwise specified, AEs will be summarized by system organ class (SOC) and preferred term (PT), with SOCs presented in the standard international order and PTs within SOCs will be presented in descending order of subject incidence.

A treatment-related TEAE is defined as TEAE which was suspected to be related to the study drugs.

AEs and marked abnormalities will be summarized by subject incidence and EAIR for the placebo-controlled phase (Weeks 0 to 16) and for the Apremilast-exposure period. In addition, selected summaries for the active treatment phase (Weeks 16 to 32) and the observational follow-up phase (4 weeks) will be presented.

An overall summary of the following AE categories will be provided.

- TEAE
- TEAE related to study drug
- Severe TEAE
- Serious TEAE
- Serious TEAE Related to Study Drug
- TEAE leading to dose reduction
- TEAE leading to drug interruption
- TEAE leading to drug withdrawal
- TEAE leading to death

In addition, for apremilast-exposure period overall summary of TEAEs will also be provided.

Tables summarizing the incidence of TEAEs by SOP and/or PT will be generated for each of the following:

- All TEAEs
- Most frequent TEAEs (subject incidence $\geq 5\%$ or another cut-off if justified)
- Treatment-related TEAEs
- TEAEs by maximum severity
- Serious TEAEs and treatment-related serious TEAEs
- TEAE leading to dose reduction
- TEAE leading to drug interruption
- TEAE leading to drug withdrawal
- TEAE leading to death
- First onset and new events of TEAE by exposure interval
 - placebo controlled phase (weeks): ≤ 1 , > 1 to ≤ 2 , > 2 to ≤ 4 , > 4 to ≤ 8 , > 8 to ≤ 12 , > 12 to ≤ 16 , > 16

CC-10004 (Apremilast)

Statistical Analysis Plan. Protocol CC-10004-PPP-001

- apremilast-exposure period (weeks): ≤ 1 , > 1 to ≤ 2 , > 2 to ≤ 4 , > 4 to ≤ 8 , > 8 to ≤ 12 , > 12 to ≤ 16 , > 16 to ≤ 24 , > 24 to ≤ 32 , > 32
- TEAE for the subgroups in [Section 10.4](#)

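### The last scheduled contact (Visit 15) may be held on day 21 after the last dose, while AE recording and pregnancy reporting run to day 28 and no later contact is specified

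*Protocol*

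**What the plan says.** **Timing of the visit.** Protocol 6.3.1: "Observational Follow-up evaluation will be performed on 28 days after last dose of IP". The same section, Section 6.2.1 and Table 5 all give a ±7-day allowance. Visit 15 is the last visit in Table 5.

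**AE window.** Protocol 6.3: "All subjects will be followed for 28 days after the last dose of IP for AE reporting". Section 10.1 has all AEs recorded "until 28 days after the last dose of IP as well as SAEs made known to the Investigator at any time following" the reporting period. The AE item in the end-of-treatment list (6.2.1) reads "AE/SAE evaluation (monitored through 28 days after the last dose of IP", and the Visit 15 list in 6.3.1 repeats it. SAP 11.1 defines treatment-emergent events as "any AEs that begin or worsen on or after the first dose of IP through 28 days after the last dose of IP", or through the treatment discontinuation date if that is later. SAP 5.2.1 counts AEs from the first 28 days after the last dose in the preceding treatment phase and presents later ones separately.

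**Pregnancy.** Protocol 10.4.1 covers pregnancies on treatment or "within 28 days of the subject's last dose of IP, are considered immediately reportable events". Section 6.5.3 requires a serum test at screening and urine tests at "Baseline Visit, Visit 10 (Week 16) and Last Treatment Visit (Visit 14 [Week 32"). It adds an unscheduled urine test after a missed period. Section 6.2.1 includes a urine test at end of treatment, which also applies to subjects withdrawn early. The Visit 15 list in 6.3.1 contains no pregnancy test.

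**The concern.** The post-treatment safety windows share one end point, day 28, but the visit meant to cover them can be held up to a week before it. At that date Section 6.3.1 is at odds with itself: a visit on day 21 cannot observe the AE period that the same section says is monitored to day 28. No telephone call or other contact is described to fill the difference.

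For a subject seen early, a non-serious event starting on days 22 to 28 enters the database only if the subject volunteers it or the site makes a contact that the protocol does not describe. The psychiatric evaluation listed at Visit 15 can likewise take place on day 21.

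The planned summaries would not reveal the difference. SAP Section 11 bases subject incidence on the number of subjects, and exposure-adjusted rates on treatment duration. Neither denominator reflects how much of the 28-day tail was observed, so seven unobserved days look the same as seven event-free days.

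The pregnancy point is separate. The 28 days after the last dose fall inside the reporting period, but nothing is scheduled in them to detect a pregnancy after the end-of-treatment or early-termination test.

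**Working it through.** No sample-size or power formula applies; this is date arithmetic and a comparison of sections.

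**Inputs**
- Nominal Visit 15: day 28 after the last dose (Protocol 6.3.1)
- Allowance: ±7 days (Protocol 6.2.1, 6.3.1, Table 5)
- End of AE recording: day 28 (Protocol 6.3, 10.1)
- End of pregnancy reporting: day 28 (Protocol 10.4.1)
- Study phases: 4, 16, 16 and 4 weeks (Protocol 3.2)

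**Step 1. The plan's own figure.** 4 + 16 + 16 + 4 = 40 weeks, which agrees with the stated maximum of about 40 weeks. The follow-up phase is therefore meant to last the full 4 weeks, or 28 days.

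**Step 2. Permitted dates for Visit 15.** Earliest 28 − 7 = day 21; latest 28 + 7 = day 35.

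**Step 3. Days with no scheduled ascertainment.** For a visit on day d, the shortfall is max(0, 28 − d).
- d = 21: 28 − 21 = 7 days (days 22 to 28)
- d = 24: 28 − 24 = 4 days
- d = 28 or later: 0 days

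As a share of the window, the worst case is 7/28 = 25%.

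**Step 4. How much of the allowance is early.** The allowance covers 35 − 21 + 1 = 15 calendar days, of which 28 − 21 = 7 fall before day 28. This counts permitted dates. It does not estimate the share of subjects seen early, which the documents do not give.

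**Step 5. Scheduled pregnancy tests.** Screening, baseline, Week 16, and Visit 14 or early termination (Protocol 6.1, 6.2, 6.2.1, 6.5.3). The number scheduled after the end-of-treatment or early-termination test is 0. This rests on the lists in 6.3.1 and 6.5.3. The pregnancy row of Table 5 ends in dashes, which agrees, but its columns are not cleanly aligned in the available text.

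**Step 6. Effect of a 0/+7 allowance.** Earliest 28 + 0 = day 28; latest 28 + 7 = day 35. The shortfall in Step 3 becomes 0 for every permitted date.

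**The case against.** The strongest reply is that only the visit can move. Protocol 6.3 and 10.1 fix AE follow-up and recording at day 28 whatever the visit date, SAEs are reportable whenever they become known, and the SAP uses the same fixed window. A site that saw a subject on day 21 and then stopped AE follow-up would breach those sections. This stands. A reader might infer that the follow-up window closes a week early, or that events are missed by rule; the documents do not support either. What remains is that a duty without a contact depends on spontaneous report.

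On pregnancy, a reader might infer that exposed pregnancies go untested. That also goes too far:
- Section 6.5.3 calls for a test after a missed period and does not limit it to the treatment phase, although Section 6.2 lists it among treatment-period procedures.
- Suspected pregnancies are immediately reportable to day 28, and contraception is required for at least 28 days after the last dose.
- Subjects who stop early have an end-of-treatment evaluation as soon as possible after that decision. It includes AE, psychiatric and urine pregnancy checks, and Visit 15 follows it.

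Nor is every subject affected. The nominal visit is on day 28, and only those seen earlier have any gap. For mood changes, Section 6.5.2 already has subjects advised to contact the investigator.

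Finally, safety is descriptive, with no inferential testing. In the placebo-controlled phase the 28-day tail matters only for subjects who stop before entering the active phase. For those who continue, the gap comes after both groups have been on apremilast, so it does not bear on the comparison with placebo. This stands too, and keeps the point small.

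**Conclusion.** The concern holds as a gap in ascertainment. The ±7-day allowance and the 28-day windows do not fit together, and no contact is specified on or after day 28 when Visit 15 is early. The size is 0 to 7 days per subject, at most 25% of the window. How many subjects are affected is unknown, so 25% is a worst case for one subject and not an expected loss. The conclusion assumes that no document outside the protocol and SAP, such as a monitoring plan or site manual, requires a later contact.

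The gap mainly concerns non-serious AEs starting on days 22 to 28. The duty to record them continues, and SAEs remain reportable without a time limit.

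On pregnancy, no test is scheduled after the end-of-treatment or early-termination test, so detection through day 28 relies on missed-period testing and self-report.

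The primary endpoint, alpha, power and sample size are untouched. This is a cheap improvement to safety capture and does not threaten the trial's main conclusion.

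**What to change.** In Table 5 and Protocol 6.2.1 and 6.3.1, change the Visit 15 allowance from ±7 days to 0/+7 days. Alternatively, keep the present allowance and require a documented AE contact on or after day 28 for any subject seen earlier. Either change takes the shortfall from as much as 7 days to 0.

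The cost is a small amendment and slightly less scheduling flexibility under the first option, or an extra contact for early attenders under the second. The latest visit remains day 35, and events found after day 28 already have a place in SAP 5.2.1, which presents them separately.

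On pregnancy, ask the sponsor to reconcile the Visit 15 list in 6.3.1, the testing schedule in 6.5.3 and the 28-day reporting period in 10.4.1. The text should say how pregnancies are meant to be detected between the end-of-treatment test and day 28, and whether the missed-period test applies in that interval. The choice of testing rule is for the sponsor.
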